7. STATISTICAL METHODOLOGY

7.1 Study Patients

7.1.1 Disposition of Subjects

Disposition of subjects will be listed.

Number and percent of subjects completed protocol scheduled visits will be presented for each study period (Study drug treatment period and Observation period). Subjects who discontinued in study drug treatment period will be summarized by reasons for discontinuation.

Number and percent of all subjects, and in each protocol defined analysis population will be presented by treatment group and overall wherever applicable.

7.1.2 Demographic and Other Baseline Characteristics

Major demographic and other baseline characteristics will be listed for all subjects.

Table2. Variables related to demographic and other baseline characteristics

Category	Variable	Data format
Subject background	Sex (male, female)	Binary
	Age at consent acquisition (years)	Metric
	Weight (kg)	Metric
	Time from onset to first dose	Metric
	Pre-administration NIHSS Total Score	Metric
	Spasm	Binary
	Race	Category
	Disease type	Category
	Japan Coma Scale	Category
	Medical history	Binary
	Concomitant Medications	Binary
	Concomitant Therapy	Binary
	Person signed Informed Consent	Category

The above demographic and baseline data will be summarized by treatment group. Baseline Weight is taken from the assessments at the Screening visit. Age in years is derived birth date in the eCRF.

Demographic data and other baseline characteristics will be summarised for the SAF by treatment group and overall. The following demographic and other baseline characteristics will be reported for this study: Age, Sex, Weight, Time from onset to first dose, Pre-administration NIHSS Total Score, Spasm, Race, Disease type, Japan Coma Scale, Medical history, Concomitant Medications , Concomitant Therapy, Person signed Informed Consent.

7.1.3 Medical History

All medical history data will be listed.

The frequency and percentage of subjects will be summarised by treatment group and overall for all subjects using Preferred Term nested within System Organ Class (SOC). The summary will be sorted by International Agreed Order (IAO) for SOC and alphabetical order for PT.

If Month and/or Day of medical history start date is missing, January and/or 1 will be used. If Month and/or Day of medical history end date is missing, December and/or 31 will be used.

7.1.4 Concomitant Medications and Concomitant Therapys

All medication/therapy data will be listed.

Concomitant medications/therapys is any medications/therapys that is on-going at the time of the first dose or started after the onset of cerebral infarction. Concomitant medications/therapys with an incomplete start date but that are still ongoing at the end of the study will be considered as concomitant medications/therapys.

7.1.5 Study Medication Exposure

All exposure data will be listed.

The number of subjects with at least one dose of exposure of IMP will be summarised by treatment group and overall.

The duration of exposure in days will be calculated as:

- 1) In the case of IMP Exposure for Continuous infusion dosing regimen(hours)

Actual dosing hours =

(Date and time of last bolus dose – Date and time of first bolus dose) +
sum of (Date and time of last div dose – Date and time of first div dose)

- 2) In the case of IMP Exposure for Approved dosing regimen(days)

Actual dosing days = Date of last dose – Date of first dose +1

If either the date of last dose or the date of first dose cannot be determined then the duration calculation will not be done. The duration of exposure will be summarised by treatment group and overall.

7.1.6 Compliance

All compliance data will be summarised.

The compliance will be calculated as:

- 1) In the case of IMP Exposure for Continuous infusion dosing regimen
Actual dosing hours / 72 hours × 100
- 2) In the case of IMP Exposure for Approved dosing regimen
Actual dosing days / 14 days or 15 days × 100,
where if first dose is evening, then the denominator will be 15 days. Others are 14 days.

7.2 .Efficacy Assessment

7.2.1.1 Adjustment for Covariates

Adjustment for covariates will not be performed.

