5.3.2 Method of Randomization and Allocation

Subjects whose eligibility based on the inclusion/exclusion criteria is confirmed will be randomly assigned to 3 treatment groups (Groups H, L, and control). At this time, subjects will be randomly assigned to either the H group, the L group, or the control group in a ratio of 5:4:5 by the stratified block method, using "NIHSS score at enrollment (NIHSS score of 4 to 9/10 to 15/16 -22)" which is considered to affect the evaluation of drug efficacy, as the stratification factor. Randomization will be based on the randomization key code table prepared by the contract randomization organization.

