13.3 Statistical and Analytical Plans

13.3.1 Efficacy

(1) Analysis of the primary endpoint

1) Primary Analysis

Changes in NIHSS over 7 days after the onset (measured daily from baseline to Day 7) will be compared by a survival analysis with "NIHSS improvement by ≥ 4 points" at the evaluation time point as an event. The comparison between the H group and the control group will be performed first, then the comparison between the L group and the control group will be performed only if a statistically significant result is obtained. The definition of censoring will be specified in the statistical analysis plan. A stratified log-rank test stratified by randomization factors will be used for the test.

2) Secondary Analyses

As survival time analysis, between-group comparison will be performed using a Cox regression model with groups and allocation factors as covariates, and the hazard ratio, its 95% confidence interval, and p-value will be presented.

(2) Analysis of secondary endpoints

1) NIHSS

For NIHSS on Day4, Day7, Day10, Day14, Week 3, discharge, and Month 3, descriptive statistics, treatment differences, and their 95% confidence intervals will be calculated for each group.

2) mRS

For mRS at 3 weeks, at discharge, and at 3 months, the proportion of mRS 0 or 1 at each measurement time point and the between-group difference in the proportion and its 95% confidence interval will be calculated.

3) BI

For the total BI score (0~100) on Day14, Week 3, at discharge, and at 3 months, descriptive statistics, inter-group differences, and their 95% confidence intervals should be calculated.

In addition, the proportion will be categorized based on the BI score, and the proportion at each measurement time point and the between-group difference in the proportion and its 95% confidence interval will be calculated.

4) FIM

For the total FIM score (18~126 points) measured at Week 3, discharge, and Month 3, descriptive statistics, inter-group differences, and their 95% confidence intervals will be calculated.

Descriptive statistics and between-group differences with their 95% confidence intervals will be calculated for the scores for the motor (13~91 points) and cognitive (5~35 points) items.

5) Time to start rehabilitation

Descriptive statistics of each group (start date of rehabilitation - date of hospitalization) and

between-group differences with their 95% confidence intervals will be calculated.

6) Duration of hospitalization

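### SAP 7.2.1.1 rules out all covariate adjustment although enrolment NIHSS is the sole randomisation stratum, leaving BI, FIM and mRS shown by arm with no reference to entry severity in a sample cut short

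*SAP*

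**What the plan says.** Protocol 5.3.2 allocates subjects to H, L and control "in a ratio of 5:4:5 by the stratified block method". The only factor is enrolment NIHSS in three bands (4-9, 10-15, 16-22), "which is considered to affect the evaluation of drug efficacy, as the stratification factor".

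Protocol 13.3.1(1) uses that factor where it tests the primary endpoint: "A stratified log-rank test stratified by randomization factors will be used for the test". The supporting analysis is "a Cox regression model with groups and allocation factors as covariates". For the secondary endpoints, 13.3.1(2) asks for between-group differences with 95% intervals (for NIHSS, "descriptive statistics, treatment differences, and their 95% confidence intervals will be calculated for each group") and names neither a baseline nor a stratum term.

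The SAP was written after recruitment was stopped. Its Introduction calls the findings exploratory, and Section 8 says efficacy will be summarised descriptively without formal tests. Section 7.2.1.1 says "Adjustment for covariates will not be performed" and gives no reason. Sections 7.2.2 and 7.2.3 list per-arm statistics only: NIHSS values and changes from baseline, the proportion improving by 4 or more NIHSS points, the mRS distribution, BI and FIM scores, and so on. Section 7.1.2 tabulates pre-administration NIHSS by arm.

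**The concern.** The design treats entry severity as important enough to stratify on, and the analysis plan then makes no use of it in estimation. By-arm tables from a randomised trial are read as comparisons, whatever they are called. If the arms differ by chance in entry NIHSS, that difference passes into the raw follow-up scores.

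This matters more after an early stop. The ratio 5:4:5 has no common divisor, so a full block holds at least 14 subjects and each of the three strata can end mid-block.

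BI, FIM and mRS are the exposed endpoints. The schedule has no pre-treatment BI or FIM, and the only earlier mRS is the pre-onset value, which says nothing about the severity of this stroke. Baseline NIHSS is therefore the one scheduled score against which these outcomes could be referenced. At stake is the readability of exploratory results. No test, error rate or sample size is affected.

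**Working it through.** **The plan's own figure.** 336 × 5/14 = 120, 336 × 4/14 = 96, 336 × 5/14 = 120. The split in protocol 6.1 agrees with 5:4:5. The SAP gives no achieved sample size.

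**Assumptions, because the documents give no values.** Strata 55/27/18%; block size 14; outcome SD 6; correlation ρ between baseline NIHSS and outcome 0.5 to 0.7; 336, 56 or 28 subjects randomised.

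**1. How far baseline severity drifts between arms.** Simulating stratified blocks under these assumptions, the SD of the chance H-control difference in baseline NIHSS is about 0.9 points at 56 subjects (above 1 point in about 25% of trials). At 28 subjects it is about 1.6 to 1.7 (above 1 point in about 54%).

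**2. What adjustment removes.** In outcome-SD units, with n per arm in H and control:
- variance of the raw difference ≈ (1 − ρ²)(2/n) + ρ²(d/s)², where d is the SD from step 1 and s is the SD of baseline NIHSS;
- variance after adjustment ≈ (1 − ρ²)(2/n), ignoring the small cost of estimating the slope.

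For s, assume scores spread evenly within strata. The stratum means are 6.5, 12.5 and 19, and the overall mean is 10.37. The within-stratum variance is 0.82 × 2.917 + 0.18 × 4 = 3.11. The between-stratum variance is 0.55 × 3.87² + 0.27 × 2.13² + 0.18 × 8.63² = 22.87. So s = √25.98 = 5.10.

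| N (n per arm) | ρ | Raw variance | Adjusted variance | Fall in SD |
|---|---|---|---|---|
| 56 (20), d = 0.89 | 0.5 | 0.075 + 0.0076 | 0.075 | 5% |
| 56 (20), d = 0.89 | 0.7 | 0.051 + 0.0149 | 0.051 | 12% |
| 28 (10), d = 1.67 | 0.5 | 0.150 + 0.0268 | 0.150 | 8% |
| 28 (10), d = 1.67 | 0.7 | 0.102 + 0.0525 | 0.102 | 19% |

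Full simulation gives 5-13% and 8-19%. At 336 subjects it gives a true SE of 0.70 (ρ 0.5) or 0.59 (ρ 0.7) raw, against 0.67 or 0.55 adjusted: 1 − 0.67/0.70 = 4% and 1 − 0.55/0.59 = 7%, or about 3-7% across runs. A repeat with scores spread evenly within strata and the slope estimated gave 2-6%, 4-11% and 6-17% at the three sizes. The ranges are therefore approximate, good to two or three percentage points.

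**3. What would happen to an unadjusted interval, if one were reported.** At 336 subjects the usual unadjusted SE averages 0.78 (ρ 0.5) or 0.79 (ρ 0.7), larger than the true 0.70 or 0.59. Coverage of a nominal 95% interval = 2Φ(1.96 × 0.78/0.70) − 1 = 97.1%, and 2Φ(1.96 × 0.79/0.59) − 1 = 99.1%. A second simulation with a right-skewed baseline gave 97.3% and 98.4%. The half-width at 120 per arm is 1.96 × √(2/120) = 0.253 SD. Multiplying by √(1 − ρ²) gives 0.219 or 0.181, which is 13% or 29% narrower. Most of that narrowing corrects an overstated SE; the fall in real noise is the 3-7% in step 2.

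**4. What NIHSS already has.** With equal SDs at both times, the variance of a change score relative to the raw score is 2(1 − ρ): 1.0 at ρ 0.5 and 0.6 at ρ 0.7. ANCOVA relative to change is (1 − ρ²)/[2(1 − ρ)] = (1 + ρ)/2: 0.75 and 0.85. Beyond the change score, adjustment would remove a further 15-25% of variance for NIHSS. BI, FIM and mRS have no such summary.

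**The case against.** The strongest reply is that a plan with no model, test or contrast has nothing to adjust, so 7.2.1.1 simply follows from the descriptive status declared in the SAP Introduction and Section 8. A per-arm mean is not wrong because it is unadjusted. Much of this stands, and it rules out several stronger readings.

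- A reader might infer that the planned efficacy intervals ignore the stratified design. The current SAP calculates none, and the protocol's primary test and Cox model both use the stratum. The coverage figures bear only on the protocol's secondary differences. Even there, lack of adjustment is inferred from silence, and the error is conservative.
- A reader might infer that entry severity is ignored throughout. For NIHSS it is not: change from baseline and the 4-point responder proportion are both referenced to baseline, and baseline NIHSS is shown by arm. The responder proportion still depends on entry score, since a subject entering at 4 must reach 0 to count.
- A reader might infer that Section 8 conceals the loss of stratification. The factor appeared only in the log-rank and Cox analyses, and the statement that efficacy is descriptive only largely discloses that both are gone.

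The reply does not cover BI, FIM and mRS. An adjusted mean is itself descriptive and needs no test, and tabulating baseline NIHSS reveals an imbalance without allowing for it. Section 8 also does not say expressly that the protocol's differences and intervals are dropped, while SAP Section 13 keeps display formats for confidence intervals and p-values.

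Sparse data limit the remedy. At 28 subjects an 18% stratum holds 28 × 0.18 = 5 subjects, or 5 × 5/14 ≈ 1.8 in each of H and control, so stratum-specific proportions and Mantel-Haenszel pooling cannot be required.

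**Conclusion.** The concern holds in a limited form. The blanket exclusion in SAP 7.2.1.1 leaves BI, FIM and mRS without any summary referenced to entry severity, although the design's only stratification factor is scheduled for every subject and adjusted means would need no test. The real gain in precision for the H-control difference is about 3-7% of its SD at 336 subjects, 5-13% at 56 and 8-19% at 28. These figures rest on assumed stratum shares, block size and correlation, and the two smaller sizes are illustrations because the achieved number is not given. No result that the SAP plans to report is invalid, and no conclusion rule changes. It is an inexpensive improvement, together with one clarification in Section 8.

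**What to change.** 1. Keep the raw summaries. Replace 7.2.1.1 with a statement that NIHSS, BI and FIM arm means will also be shown adjusted for continuous baseline NIHSS (ANCOVA with arm and baseline NIHSS), descriptively and without tests.
2. Show the 4-point NIHSS responder and mRS 0-1 proportions by randomisation stratum only where numbers allow.
3. If any between-group difference with a 95% interval from protocol 13.3.1(2) is reported, include baseline NIHSS or the stratum in it. If none is, state in SAP Section 8 that those differences and intervals are dropped, and remove the unused interval and p-value formats from Section 13.

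The cost is SAP wording and some extra table columns, with no new data. The downside is that adjusted means of bounded scores in small arms depend on the model, so they belong beside the raw values and not in place of them. If the change is made after data lock, protocol 13.4 requires the reason to be given and the results kept distinct from the planned analysis.

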7.2.1.2 Handling of Dropouts or Missing Data

Unless otherwise specified, data will be used to their maximum possible extent, but without any imputations for missing data, i.e. missing values will not be replaced or estimated.

7.2.1.3 Interim Analyses and Data Monitoring

No interim analysis will be performed for this study and therefore no adjustment on type 1 error will be made.

7.2.1.4 Multicentre Studies

Due to the low number of subjects by centre, a centre effect was not included in any of the statistical analyses.

7.2.1.5 Multiple/Comparisons/Multiplicity

The study is not powered to address multiple statistical comparisons; therefore no adjustment for multiplicity will be made.

7.2.1.6 Use of an 'Efficacy Subset' of Patients

Not applicable in this study.

7.2.1.7 Active-Control Studies Intended to show equivalence

Not applicable in this study.

7.2.1.8 Examinations of Subgroups

Not applicable in this study.

7.2.2 Primary Efficacy Endpoint

NIHSS (change over the 7 days from onset)

NIHSS value and changes from baseline will be summarized descriptively by treatment group and analysis visit.

7.2.3 Secondary Efficacy Endpoints

- (1) NIHSS (Day 4, Day 7, Day 10, Day 14, after 3 weeks, at discharge, after 3 months)
- (2) mRS (after 3 weeks, at discharge, after 3 months)
- (3) BI (Day 14, after 3 weeks, at discharge, after 3 months)
- (4) FIM (after 3 weeks, at discharge, after 3 months)
- (5) Start of rehabilitation
- (6) Duration of hospitalization
- (7) Cranial imaging diagnosis

1) NIHSS

The descriptive statistics will be calculated for the NIHSS scores at Day 4, Day 7, Day 10, Day 14, after 3 weeks, at discharge, and after 3 months. The number and percentage of patients with an improvement of 4 or more points in the NIHSS score will be summarized by treatment group and analysis visit.

2) mRS

The number and percentage of patients with mRS each score (0, 1,...,6) after 3 weeks, at discharge, and after 3 months will be summarized by treatment group.

3) BI

The descriptive statistics for each treatment group will be calculated for the total BI score (0 to 100) at Day 14, after 3 weeks, at discharge, and after 3 months. The number and percentage of patients for BI three categorical score (100-95, 90-55, 50-0) will be summarized by treatment group and analysis visit.

4) FIM

The descriptive statistics for each treatment group will be calculated for the FIM total scores (18 to 126 points) measured after 3 weeks, at discharge, and after 3 months.

The descriptive statistics will also be calculated for the motor item (13 to 91 points) and cognitive item (5 to 35 points) scores.

5) Time of rehabilitation initiation

The descriptive statistics for each treatment group will be calculated for the time of rehabilitation initiation (the start date of rehabilitation minus the start date of hospitalization + 1).

6) Duration of hospitalization

The descriptive statistics for each treatment group will be calculated for the duration of hospitalization (the start date of discharge minus the start date of hospitalization + 1).

(7) Cranial imaging diagnosis

Image analysis

(i) Infarct volume

The descriptive statistics for each treatment group will be calculated for the infarct volume.

(ii) Severity of cerebral edema

The change in the edema will be calculated, and descriptive statistics for each treatment group will be calculated.

(iii) Presence or absence of intracranial bleeding

The proportion of subjects with intracranial bleeding will be calculated by severity, and the descriptive statistics for each treatment group will be calculated.

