8. CHANGES FROM THE PROTOCOL

MTPC has decided that this study is prematurely terminated due to reconsideration of the MTPC's product pipeline. Therefore, the stasitical analysis plan is changed form the protocol as follows.

- Per protocol set will be excluded from the analysis populations.
- Efficacy endpoints will be only descriptively summarized without any formal statististical test.

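### No planned SAP output gives the cumulative proportion or timing of first 4-point NIHSS improvement to Day 7, the form of the protocol's primary analysis, and SAP Section 8 does not say it was dropped

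*SAP*

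**What the plan says.** **Protocol.** Sections 5.4.1 and 9.2.3 name NIHSS over 7 days as the primary endpoint and require a score every day from Day 1 to Day 7. Under the primary analysis in 13.3.1, changes in these daily scores "will be compared by a survival analysis with 'NIHSS improvement by ≥ 4 points' at the evaluation time point as an event". The same section adds: "A stratified log-rank test stratified by randomization factors will be used for the test". A Cox model with hazard ratio and 95% confidence interval follows as a secondary analysis. On censoring: "The definition of censoring will be specified in the statistical analysis plan".

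**SAP.**
- 7.2.2, the primary endpoint: "NIHSS value and changes from baseline will be summarized descriptively by treatment group and analysis visit".
- 7.2.3, under the secondary endpoints: "The number and percentage of patients with an improvement of 4 or more points in the NIHSS score will be summarized by treatment group", broken down by analysis visit. Table 14.2.1.1 is the matching output.
- Section 8 lists two changes from the protocol. One removes the per-protocol set. The other reads: "Efficacy endpoints will be only descriptively summarized without any formal statististical test".
- Section 6 and Appendix 1 set the visit windows. When several values fall in one window, the value nearest the planned day is used.

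**The concern.** The protocol asks who reached a 4-point improvement within the first week, and how soon. The SAP keeps the 4-point threshold but counts patients by their status on each visit day. A patient who is 4 points better on Day 3 and 3 points better on Day 7 has had the event under a survival analysis, yet is a non-improver in the Day 7 row.

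The trial was stopped early and its results are declared exploratory, so dropping the log-rank test is understandable. That does not explain why the quantity the test was to compare is missing as well. A reader of the study report would probably take the Day 7 percentage as the primary result, although it answers a different question. The change log would not say that the time-to-event form had gone.

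**Working it through.** The documents give no event rate, and the sample-size rationale is blacked out, so there is no figure to reproduce. The check is mainly a comparison of texts.

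**1. What the protocol's analysis needs.** It needs, for each patient, the day of first improvement of 4 or more points on Days 1 to 7, or a censoring day. The word *first* is not written. It follows from using a survival analysis with censoring on repeated daily scores.

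**2. What the SAP delivers.**

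| Element | Protocol 13.3.1 | SAP |
|---|---|---|
| Primary summary | Time to 4-point improvement | NIHSS value and change by visit (7.2.2) |
| 4-point criterion | Event in the survival analysis | Status at each analysis visit (7.2.3, Table 14.2.1.1) |
| Censoring | Left to the SAP | No rule |
| Cumulative proportion or curve | Part of the method | No such table; no figure listed in Section 14 |
| Cox hazard ratio | Planned | Absent |

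**3. The Day 6 score.** Appendix 1 has no Day 6 analysis visit for NIHSS. The [4, 6] window attached to Day 4 is for imaging. Day 6 falls in the Day 7 window, [6, 8], where a Day 7 score is closer to target and replaces it. An improvement seen only on Day 6 therefore appears in no by-visit table if Day 7 was scored.

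**4. Why by-visit percentages do not recover the endpoint.** Let C be the proportion of an arm that ever improves by 4 or more points by Day 7, and r the share of those no longer improved at Day 7. With everyone scored at Day 7 on that day:

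Day 7 percentage = C × (1 − r)

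The table would show the left side only, so C and r cannot be separated. These values are assumptions, chosen to show the range:

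- C = 50% and r = 5%, 10%, 20%, 30% give 47.5%, 45%, 40%, 35%.
- Equal C of 50% in two arms, with r = 5% and 20%: 47.5% against 40%, an apparent difference of 7.5 points where the cumulative difference is zero.
- C = 50% and 40%, with r = 30% and 10%: 0.50 × 0.70 = 35% against 0.40 × 0.90 = 36%. A 10-point cumulative difference has vanished.
- r = 0: the Day 7 percentage equals C.

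**5. Direction.** SAP Section 6 uses the full group as denominator by default but allows subjects with available data instead. Nothing says which applies to Table 14.2.1.1. With N subjects, of whom m event-free subjects have no Day 7 score, the available-data percentage is N × C × (1 − r) / (N − m). It exceeds C when m > N × r. For the planned N = 120 (H or control) and r = 5%, the threshold is 120 × 0.05 = 6. At C = 50% and m = 6 the result is 120 × 0.50 × 0.95 / 114 = 57 / 114 = 50%, equal to C. With more than 6 such subjects, the Day 7 percentage is above the cumulative proportion. A Day 8 score can also enter the Day 7 row when Day 7 is missing.

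**The case against.** The strongest case on the other side has four parts.

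- **The endpoint was not replaced.** A reader might infer that the SAP substituted mean change for the protocol's primary endpoint. The documents do not support that. The protocol's named endpoint is NIHSS over 7 days, with comparison of the time course as its rationale, and SAP 2.2 names nearly the same thing. What changed is the analysis. Nor is the SAP limited to means: Section 6 specifies n, mean, SD, median, minimum and maximum. This stands.
- **The change is partly disclosed.** SAP Sections 1 and 8 say openly that recruitment stopped for pipeline reasons, that results are exploratory and that efficacy is descriptive. This covers the log-rank test and p-values. It does not cover the time-to-event form, because a count of patients with a first event, or a Kaplan-Meier curve, is itself descriptive. Protocol 13.4 asks that changes to the analysis be given with their reason in the SAP.
- **The information is nearly there.** The 4-point criterion heads the efficacy tables, Listing 16.2.5.1 gives individual scores, and Section 14 calls its list a minimum. With no slip-back and no missing scores, the by-visit rows would trace the cumulative curve apart from Day 6. But a listing is not a summary by arm, and Section 14 also says that a complete list should be included.
- **No confirmatory inference is at stake.** This is true, and it limits the weight of the point without removing it.

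**Conclusion.** The point holds as a reporting and disclosure gap. No planned output gives, by arm, the cumulative proportion or the timing of first 4-point improvement to Day 7. Day 6 scores can drop out of the by-visit tables, the censoring rule that the protocol left to the SAP is absent, and Section 8 does not record the loss of the time-to-event form. This rests on one inference: that the protocol's survival analysis means time to first improvement.

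A reader might go further and say that the Day 7 percentage understates the protocol's event rate by some known amount. The documents do not support this. They give no event rate and no measure of day-to-day scoring variation. If improvement is steady and scored without fluctuation, the cumulative and Day 7 proportions coincide. A simulated loss would therefore mainly hand back the variation assumed for it. The direction is not assured either, since it depends on the denominator and on who is missing at Day 7.

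For a terminated, exploratory study this is a modest correction, and worth making because it restores the quantity the protocol set out to analyse.

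**What to change.** 1. In SAP 7.2.2 and the Section 14 table list, add by treatment group in the FAS the number and percentage of subjects whose first NIHSS improvement of 4 or more points from baseline occurs on Day 1 to Day 7. Derive it from all daily scores, including Day 6, and not from the windowed visits.
2. Add a descriptive Kaplan-Meier or cumulative incidence summary by arm, with the median day if reached. State the rule for censoring, death and discontinuation. The protocol left this rule to the SAP and more than one choice is defensible, so what matters is that it is written down before unblinding.
3. State the denominator for the percentages in Table 14.2.1.1.
4. In Section 8, state that the log-rank and Cox analyses are dropped, and that the by-visit summaries are additional to the protocol's primary analysis.

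No test is needed. The scores are already collected daily, so the cost is a few lines of text, one derived variable and one table or figure.
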